4.1.1 Inclusion Criteria

Patients must meet the following criteria for study entry:

- Written informed consent for study participation obtained from patient's parents or legal guardian, with assent as appropriate by the patient, depending on the patient's level of understanding
- Age at screening between ≥ 2 and < 18 years
- Diagnosis of GPA (EULAR/PRINTO/PRES 2008, Ankara criteria for childhood WG [Özen et al. 2010]; see [Appendix 5](#)) or diagnosis of MPA (according to the Chapel Hill Consensus Conference [Jennette 1994]; see [Appendix 6](#))
- Newly diagnosed patients or patients with relapsing disease according to the following definition:
 - The recurrence or new onset of potentially organ- or life-threatening disease (i.e., one or more major BVAS/WG items listed in [Table 3](#) or disease severe enough to require treatment with CYC).
- For patients of reproductive potential (males and females), use of a reliable means of contraception (e.g., abstinence, hormonal contraceptive patch, intrauterine device, physical barrier) throughout their study participation

- For all eligible patients, mandatory prophylactic treatment for *Pneumocystis jiroveci* infection

Table 3 BVAS/WG Features of Limited and Severe AAV

Severe (Major) BVAS/WG Items ^a	Limited (Minor) BVAS/WG Items ^b
Cutaneous gangrene	Arthralgias/arthritis
Scleritis	Fever (> 38°C)
Retinal exudates/hemorrhage	Purpura
Sensorineural hearing loss	Skin ulcer
Mesenteric ischemia	Mouth ulcers
Alveolar hemorrhage	Conjunctivitis/episcleritis
Red blood cell urinary casts	Orbital mass/proptosis
Rise in serum creatinine 30% over baseline value	Uveitis
Aseptic meningitis	Bloody nasal discharge/nasal crusting
Spinal cord lesions	Sinus involvement
Cerebrovascular accident caused by vasculitis	Swollen salivary gland
Cranial nerve palsy	Subglottic inflammation
Sensory peripheral neuropathy	Conductive deafness ^c
Motor mononeuritis multiplex	Pericarditis
	Pleurisy
	Pulmonary nodules or cavities
	Other pulmonary infiltrates secondary to vasculitis
	Endobronchial lesions
	Hematuria

AAV=ANCA-associated vasculitis; ANCA=anti-neutrophil cytoplasmic antibody
 BVAS=Birmingham Vasculitis Activity Score; WG=Wegner's granulomatosis.

^a Any of these items must be attributable to the active underlying disease.

^b Minor items with a significant risk of morbidity may be classified as severe (i.e., BVAS/WG 3).

^c Additional testing may be required to make the diagnosis.

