4.3.2 Dosage, Administration, and Compliance

4.3.2.1 Rituximab (Investigational Medicinal Product)

4.3.2.1.1 Dosage and Administration

For this trial, rituximab will be given as an IV infusion of 375 mg/m² once a week for 4 consecutive weeks, starting at the baseline visit. The dose for rituximab will be calculated according to the participant's BSA at the screening visit after the participant's eligibility has been established, and it will remain the same for all four infusions. Each participant's actual body height and weight, measured during the 28-day period before baseline (i.e., during the 28 days before the start of administration of open-label rituximab) will be used to calculate a patient's BSA according to the Dubois formula ([DuBois and Dubois 1916](#)):

$$\text{BSA (m}^2\text{)} = [(\text{Weight in kg})^{0.425} \times (\text{Height in cm})^{0.725}] \times 0.00718$$

Note: Do not round until the end of the calculation.

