4.3.2.3 Prednisolone or Prednisone (Non-Investigational Medicinal Product)

4.3.2.3.1 Dosage, Administration, and Compliance

On Day 1 and following completion of IV glucocorticoids, all patients will receive concomitant oral prednisolone or prednisone (1 mg/kg/day or up to 60 mg/day or equivalent, whichever is lower), the dose of which will be tapered to a minimum of 0.2 mg/kg/day (or 10 mg/day, whichever is the lowest) no later than Month 6.

The general guidance on the suggested oral steroid dose-tapering schedule is to taper from 1 mg/kg/day (60 mg/day, maximum) at the start of treatment, to 0.8 mg/kg/day by Month 1, and then by 0.1–0.2 mg/kg/day each month to 0.2 mg/kg/day (or 10 mg/day, whichever is the lowest), which should be reached no later than Month 6.

Oral prednisone (used in some non-UK sites) may be substituted for prednisolone at the same dose as long as there is no hepatic impairment.

The steroid-tapering practice is specific to a particular patient and as such should be tailored individually for each patient at the time of study entry, at the discretion of the investigator.

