
ID: EX001.1SP
 
Summary of Rituximab Exposure
	
STREAM Template: None
 
Analysis Population: Safety Evaluable Population
 
Analysis Variables: See mock. Percentages are based on n. Include data from Day 1 to common closeout date.
 
- study end date =
 
 1. For early discontinuation or completion patients: minimum of or early withdrawal/discontinuation or patient completed study 2. For the rest of patients: minimum of common closeout date and last known alive date 
Duration of observation = study end date – study start date + 1.
 
Date of last contact is the last available date of efficacy, complete medication start date, laboratory, adverse event assessments, early withdrawal visit, date of last contact or date of death.

---	---

Total number of Infusions administered	
n	nn
Mean (SD)	xxx.x (xx.x)
Median	xx.x
Q1-Q3 (IQR)	xx.x-xx.x (xx.x)
Min - Max	xx - xxx
Total cumulative dose (mg)	
n	nn
Mean (SD)	xxx.x (xx.x)
Median	xx.x
Q1-Q3 (IQR)	xx.x-xx.x (xx.x)
Min - Max	xx - xxx
Duration of Observation (Months)	
n	nn
Mean (SD)	xx.x (xx.x)
Median	xx.x
Q1-Q3 (IQR)	xx.x-xx.x (xx.x)
Min - Max	xx.x - xx.x
Duration of Observation (Months)	
n	nn
Duration ≤ 6	nn (xx.x%)
6 < Duration ≤ 12	nn (xx.x%)
12 < Duration ≤ 18	nn (xx.x%)
18 < Duration ≤ 24	nn (xx.x%)
24 < Duration ≤ 36	nn (xx.x%)
36 < Duration ≤ 48	nn (xx.x%)
48 < Duration ≤ 60	nn (xx.x%)
Duration > 60	nn (xx.x%)
Total patient years of observation	xxx.xx

ID: EX001.2SP

STREAM Template: None

Rituximab
Administration over
Course of study

[figure not shown]
Analysis Population: Safety Evaluable Population

Plot of:

Y-Axis: Patient ID

X-Axis: Study Visit

See mockup.

ID: EX002SP

Listing of Rituximab Administrations, Interruptions and Modifications

STREAM Template: None

Analysis Population: Safety Evaluable Population

Column Variables: Include data from Day 1 to common closout date.

Add "Dose Administered" column in "mg/m²" calculating as follows:

administered dose (mg/m²) = dose administered (mg) / BSA (m²),

where

$$BSA = \text{body surface area} = \text{sqrt} [BW \times Ht / 3600]$$

BW = weight (kg)

Ht = height (cm)

See mockup

Sorting: Sort by center / patient ID and treatment administration day.

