Center / Patient ID	Age/Sex/Race	Height (cm) / Weight (kg)	Target Day	Study Day	Study Visit	Planned Dose (mg)	Dose Administered (mg)	Dose Administered (mg/m ²)	Volume Administered (mL)	Infusion Interrupted / Modified	Reason for Modification
ASL.SITEID/AE.PATNUM	ASL.AGE/ASL.SEX/ASL.RACE										
████████	████████	████████	1	1	baseline	xxx	478.8	xxx	xxx	No	
			8	8	week 2	xxx	479.2	xxx	xxx	No	
			15	15	week 2	xxx	479.2	xxx	xxx	Yes	Medication Error
			22	22	month 1	xxx	482.5	xxx	xxx	No	
...											

ID: EX003SP
 
Corticosteroid Treatment Exposure during Remission Induction Phase and Overall
	
STREAM Template: EXT01
 
Analysis Population: Safety Evaluable Population
 
Analysis Variables: Oral steroids: duration of use and total dose.
 
All steroids (all route) total use. This needs discussing with [REDACTED] as she has indicated that she will not be able to supply conversion factors for non-oral steroids.
 
Percentages are based on n.

---	---

Phase: ...

Rituximab
(N=25)

ORAL CORTICOSTEROID DRUGS

Treatment duration (D)

n	25
Mean (SD)	xxx.x (xx.x)
Median	xx.x
Q1 - Q3 (IQR)	xx.x - xx.x (xx.x)
Min - Max	xx - xxx

Treatment duration

n	nn
<1 month (1-25 days)	nn (xx.x%)
1 - <2 months (26-44 days)	nn (xx.x%)
2 - <4 months (45-104 days)	nn (xx.x%)
4 - <6 months (105-164 days)	nn (xx.x%)
6 months (>=165 days)	nn (xx.x%)

Total cumulative oral dose(mg)

n	nn
Mean (SD)	xxx.x (xx.x)
Median	xx.x
Q1 - Q3 (IQR)	xx.x - xx.x (xx.x)
Min - Max	xx - xxx

ALL CORTICOSTEROID DRUGS

Total cumulative dose(mg)

n	nn
Mean (SD)	xxx.x (xx.x)
Median	xx.x
Q1 - Q3 (IQR)	xx.x - xx.x (xx.x)
Min - Max	xx - xxx

ID: EX004SP
 
Listing of Steroid Use
	
STREAM Template: None
 
Analysis Population: Safety Evaluable Population
 
Variables Displayed: See mockup.
 
Sorting: Sort by center / patient ID and treatment administration day.

--	--

Center / Patient ID	Age/Sex/Race ASL.AGE/ ASL.SITEI D/AE.PAT NUM	Height (cm) / Weight (kg) ASL.SEX/ ASL.RACE	Start Day	End Day	Medication	Dose Administered	Unit	Route
██████████	██████████	██████████	1	1	DEXAMETHASONE *	8	mg	Intravenous
			8	9		479.2		
			15	15		479.2		
			22	22		482.5		
██████████	██████████	██████████	1	1		322.5		
			8	8		322.5		
			15	15		322.5		

* GPA/MPA, PRE-RITUXIMAB INFUSION AND GLUCOCORTICOID CONCOMITANT MEDICATIONS

ID: EX006SP

Methylprednisolone
Treatment Exposure
During Screening
Period Prior to **First**
Rituximab Infusion

STREAM Template: EXT01

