Analysis Population: Safety Evaluable Population

Analysis Variables: See mockup.

Methylprednisolone (30 mg/kg, up to 1 g/day)
include Methylprednisolone dose on or before Day 1
for the number of doses, include number and percentage of patients
having 1, 2, 3 and >3 doses.

Statistics and Calculation Methods: Percentages are based on n.

[figure not shown]
Sorting: Sort by center / patient ID and treatment administration
day.

	Rituximab (N=nnn)
Treatment duration (D)	
n	nn
Mean (SD)	xx.x (xx.x)
Median	xx.x
Q1-Q3 (IQR)	xx.x-xx.x (xx.x)
Min-max	xx-xx
Number of doses	
n	nn
1 dose	xx.x (xx.x%)
2 doses	xx.x (xx.x%)
3 doses	xx.x (xx.x%)
> 3 doses	xx.x (xx.x%)
Total cumulative dose (mg)	
n	nn
Mean (SD)	xx.x (xx.x)
Median	xx.x
Q1-Q3 (IQR)	xx.x-xx.x (xx.x)
Min-max	xx-xx

ID: EX007SP
 
Patient Profile of Oral Steroid Use
	
STREAM Template: None
 
Analysis Population: Safety Evaluable Population
 
Plot of:
 
Y-Axis: Daily prednisolone equivalent dose (mg)
 
X-Axis: Study Visit
 
One plot for each patient.
 
Reference lines: Draw reference lines through the x-axis on the days of RTX administration.

--	---

Patient Profile of Oral Steroid Use, Safety-Evaluable Patients
Protocol: WA25615

[figure not shown]
Treatment Group: RITUXIMAB (N=25) Center/Patient ID:

ID: EX007.1SP
 
Patient Profiles of Cumulative Glucocorticoid Use
	
STREAM Template: None
 
Analysis Population: Safety Evaluable Population
 
Analysis Variables: Cumulative steroid (Oral and other types in one plot with different shapes/colors) use to Months Weeks 1 to 3 and Months 1, 2, 4, 6, 12 and 18.
 
Plot of:
 
Y-Axis: Cumulative prednisone equivalent dose (mg) to time-points given above.
 
X-Axis: Study Visit
 
One plot for each patient.
 
Reference lines: Draw reference lines through the x-axis on the days of RTX administration.
 
Numeric Precision and Formatting of Statistics: see mockup.

--	--

[figure not shown]
Patient Profiles of Cumulative Oral Glucocorticoid Use, Safety-Evaluable Patients
Protocol: WA25615

Treatment Group: RITUXIMAB (N=25) Center/Patient ID:

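### The pooled rituximab and steroid dose summaries are in absolute mg, so across ages 2 to under 18 they mainly reflect body size; add size-adjusted rows

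*SAP*

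**What the plan says.** Protocol 4.3.2.1.1 sets the induction course by body surface area (BSA): "rituximab will be given as an IV infusion of 375 mg/m² once a week for 4 consecutive weeks". For the BSA, height and weight "will be used to calculate a patient's BSA according to the Dubois formula". Protocol 4.3.2.3.1 starts oral prednisolone or prednisone at 1 mg/kg/day with a 60 mg/day cap, to be "tapered to a minimum of 0.2 mg/kg/day (or 10 mg/day, whichever is the lowest) no later than Month 6". The eligible range is "Age at screening between ≥ 2 and < 18 years", and Protocol 4.5.3.5 foresees patients below 13 kg.

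SAP 5.1 specifies these exposure outputs:

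- **Rituximab, pooled:** EX001SP (induction) and EX001.1SP (Day 1 to common closeout) each have a row "Total cumulative dose (mg").
- **Steroid, pooled:** EX003SP has "Total cumulative oral dose(mg"). EX007.2SP plots median prednisone-equivalent mg. EX007.3SP tabulates use by visit and names no unit.
- **Steroid, per patient:** EX007SP has "Y-Axis: Daily prednisolone equivalent dose (mg") and EX007.1SP shows cumulative mg. Each is one plot per patient, with reference lines only on rituximab days.
- **Listings:** EX002SP gives planned mg, administered mg and administered mg/m² for each infusion, with height and weight. EX004SP gives each steroid record with height and weight.

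No visible summary gives mg/m² or mg/kg, and no visible output counts children at the Month 6 steroid level.

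**The concern.** Safety is a primary objective, and the exposure tables tell a reader how much rituximab and steroid lies behind the safety findings. When dose is set by size and the age range is wide, a mean, SD, median or range in mg mixes two things: how large the children were and how much they received relative to what was prescribed. The second is the one of interest. SAP 3.4 rules out subgroup analyses because of the sample size, so no age split would separate them.

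The gap matters most after Month 6. Protocol 4.3.4 leaves the dose and frequency of retreatment to the investigator. EX001.1SP runs to common closeout, so its mg total combines body size, number of courses and chosen dose. Infusion counts do not show dose per m² in that period.

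**Working it through.** The plan states no figure to reproduce; the check is direct arithmetic. The documents give no body sizes, so all weights and heights below are assumptions.

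**Formulas**

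- Protocol BSA = 0.00718 × kg^0.425 × cm^0.725 (Protocol 4.3.2.1.1).
- Full course in mg = 4 × 375 × BSA = 1,500 × BSA.
- Month 6 oral steroid level = lower of 0.2 × kg and 10 mg/day (Protocol 4.3.2.3.1).
- mg/m² as EX002SP would list it for a correctly dosed child = 375 × protocol BSA ÷ sqrt(kg × cm / 3600).

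**Results** (computed from unrounded BSA)

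| kg / cm | BSA, m² | Full course, mg | Month 6 level, mg/day | 10 mg/day in mg/kg | EX002SP would list, mg/m² |
|---|---|---|---|---|---|
| 10 / 80 | 0.458 | 687 | 2.0 | 1.00 | 364.3 |
| 12 / 86 | 0.522 | 782 | 2.4 | 0.83 | 365.3 |
| 20 / 115 | 0.800 | 1,200 | 4.0 | 0.50 | 375.3 |
| 40 / 150 | 1.302 | 1,953 | 8.0 | 0.25 | 378.2 |
| 50 / 162 | 1.514 | 2,271 | 10.0 | 0.20 | 378.5 |
| 65 / 172 | 1.768 | 2,651 | 10.0 | 0.15 | 376.1 |
| 80 / 178 | 1.979 | 2,969 | 10.0 | 0.125 | 373.2 |

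**Reading the results**

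1. *Rituximab in mg.* 2,651 ÷ 782 = 3.4, from size alone. Over all the assumed sizes the range is 687 to 2,969 mg, with every child fully dosed.
2. *A shortfall on the mg scale.* Three of four infusions at 65 kg/172 cm is 0.75 × 2,651 ≈ 1,988 mg, still 2.5 times the full course at 12 kg/86 cm. On the mg/m² scale it is 1,125 against 1,500, or 75% of plan.
3. *Steroid in mg.* A dose of 10 mg/day equals the Month 6 level from 50 kg upward. At 12 kg it is 0.83 mg/kg/day, and 10 ÷ 2.4 ≈ 4.2 times that child's level. Below 50 kg, mg cannot be judged against the protocol level without the weight.
4. *BSA formula.* EX002SP divides by a different BSA from the one the protocol uses for dosing. A child dosed exactly at 375 mg/m² would be listed at about 364 to 379, or −2.8% to +0.9% over these sizes. The listing would show small deviations that did not occur.

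**The case against.** A reader might infer that the tables cannot show under-dosing, or that a missed infusion in a large adolescent would go unseen. The documents do not support that. EX001SP tabulates infusions started and interrupted or modified by visit, and patients by number of infusions completed. EX001.1SP summarises infusions administered, EX001.2SP plots administrations by patient, and DS002SP counts completion of planned treatment. The dose is fixed across the four induction infusions, so a missed one appears as a count. A reduced infusion appears in EX002SP, with planned beside administered dose, and with 25 patients that listing can be read.

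A reader might also infer that EX007SP is distorted by the mix of sizes, or that attainment of the steroid level is nowhere analysed. EX007SP and EX007.1SP are one plot per patient, so there is no mixing; they lack only a size-adjusted scale or target line. The efficacy outcomes and outputs are redacted in both documents, so a steroid-level output there cannot be ruled out.

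Three further points have force. The 10 mg/day limb makes mg the relevant scale from 50 kg upward, so mg/kg should sit beside mg and not replace it. The taper is general guidance that the investigator tailors to each child. The study is exploratory and single-arm without hypothesis testing, and systemic rituximab exposure is assessed through the PK parameters, so no formal conclusion turns on these rows.

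All of this limits the point. None of it makes the pooled mg rows informative about dose relative to prescription, or gives dose per m² in any summary of discretionary retreatment.

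**Conclusion.** The point holds as a gap in the pooled summaries. The dose rows of EX001SP, EX001.1SP, EX003SP and EX007.2SP mainly reflect body size; the same applies to EX007.3SP if it is in mg. At the assumed sizes the spread between two fully dosed children is 3.4-fold, and it depends on how widely the enrolled children differ in size, which the documents do not give. The steroid comparison reads the protocol as the lower of the two limits and applies the child's current weight.

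The point does not extend to undetectable under-dosing, or to a claim that the steroid level is certainly unanalysed. The difference in BSA formula between EX002SP and the protocol is a separate inconsistency that needs reconciling. This is a cheap improvement that makes pooled exposure interpretable; it changes no estimate or test.

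**What to change.** 1. **EX001SP:** add cumulative rituximab in mg/m², or percent of planned dose, beside mg.
2. **EX001.1SP:** add mg/m² by course, using the BSA from the height and weight nearest each course. The protocol defines the dosing BSA only for the initial four infusions.
3. **EX002SP:** reconcile its sqrt(BW × Ht / 3600) formula with the protocol's DuBois formula, and state which BSA the mg/m² column uses.
4. **EX003SP, EX007.2SP and EX007.3SP:** add oral steroid in mg/kg, using the latest scheduled weight, beside mg. State the unit in EX007.3SP.
5. **EX007SP:** mark each child's existing protocol Month 6 level (lower of 0.2 mg/kg/day and 10 mg/day). Tabulate the number of children at or below it at Month 6, unless a redacted output already does.

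The schedule of assessments collects height and weight at screening, baseline and every visit from Month 1, so no new data are needed. The cost is a small amount of programming and a second line per table.

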6. ADVERSE EVENTS

Adverse events will be considered TE (defined in Section 4) irrespective of the length of time since the first RTX infusion. Only TE adverse events will be included in summary tables. The current sponsor data safety standards will be used where available.

Summaries of TE adverse events will be produced by study phase. Summaries will be produced of the numbers of patients (%) experiencing the following TE adverse events:

Summaries will be produced of the following TE adverse events:

- Summary profile of TE adverse events
- Overview of adverse events
- All events
- All events by most extreme toxicity grade^(*)
- Events other than IRR occurring during or within 24 hours of a RTX Infusion by relationship to treatment (count multiple occurrences as one event)
- Events leading to death
- SAEs
- SAEs assessed as related to the study drug
- Events leading to discontinuation of study medication
- Events leading to a study medication dose modification
 - Infections
 - MedDRA SOC infections and infestations
 - Serious Infections
 - serious events in MedDRA SOC infections and infestations (include non-serious infections treated with IV anti-infective)
 - Opportunistic Infection
 - from Roche standard AEGT Opportunistic Infections
 - Infusion Related Reactions (IRRs)
 - events that occur during or within 24 hours of an infusion and fall within Roche standard AEGT Infusion Related Reactions + Hypersensitivity
 - Count multiple symptoms as one IRR for each infusion.
 - Cardiac events
 - MedDRA SOC “Cardiac Events” MedDRA SOC “Cardiac Events”
 - Malignancies
 - preferred terms in the Malignant or Unspecified Tumors SMQ (Wide)
- CTCAE grade 3 and grade 4 events
- Non-serious events reported by $\geq 5\%$ patients (CTg requirement, not for CSR)
- Common Adverse Events reported by $\geq 10\%$ patients

^(*) Most extreme toxicity grade is recorded on the eCRF. If most extreme toxicity grade is not recorded then initial toxicity grade will be used; if neither grade is given then an unknown category will be used. The grading is based on National Cancer Institute Common Terminology Criteria for Adverse Events (NCI CTCAE), Version 4.

Adverse Event Output Specifications

ID: AE001SP	STREAM Template: AET01


ID: AE002.2SP
 
Summary of Infusion Related Reactions (IRRs) by Visit
	
STREAM Template: DMT01
 
Analysis Population: Safety Evaluable Population
 
Analysis Variables: See mockup.
 
Column Variables: Infusion numbers.
 
Statistics and Calculation Methods: Include two tables in one output file:
 
 1. For remission induction phase. 2. For overall period, Day 1 to common closeout date. 
Infusion Related Reactions (IRRs) are defined as:
 
 • events that occur during or within 24 hours of an infusion and fall within Roche standard AEGT Infusion Related Reactions + Hypersensitivity 
Count multiple symptoms as one IRR for each infusion.
 
Percentages are based on n.
 
Visits to be included: Baseline, Week 1 to 3, month 6, 12 and 18.
 
Symptom of IRR = Reported term.
 
Numeric Precision and Formatting of Statistics: See mockup

--	--

Preferred Term/ Symptom of IRR	Rituximab (N=57)				
	Infusion 1 ...	Infusion 4	Infusion 5	Infusion 8	Infusion 10
Number of patients who had an infusion (n)	57	56	56	54	54
Infusion related reaction*					
Total No. of patients with events	5 (8.8%)	1 (1.8%)	2 (3.6%)	1 (1.9%)	0
bronchospasm	1 (1.8%)	0	0	0	0
cough	1 (1.8%)	0	0	0	0
exanthema	0	0	0	1 (1.9%)	0
metallic taste, tingling at the back of the throat	0	1 (1.8%)	0	0	0
pruritus	1 (1.8%)	0	0	0	0
skin rash	1 (1.8%)	0	0	0	0
tightness in the throat	0	0	1 (1.8%)	0	0
tingling at the back of the throat during the	0	0	1 (1.8%)	0	0

ID: AE004SP to ID: AE020SP
 
Adverse Event Subsets during Remission Induction Phase and Overall
	
STREAM Template: AET02
 
Analysis Population: Safety Evaluable Population
 
Subset: Same table contents and format, except use the following subsets (see also the beginning of this section):
																										
	
  
 ID	Subset	
   
 AE005SP	Events resulting to death (Stream Template: AET07)	
 
 AE006SP	SAEs	
 
 AE007SP	SAEs assessed as related to the study drug	
 
 AE008SP	Events leading to discontinuation of study medication	
 
 AE009SP	Events leading to a study medication dose modification	
 
 AE010SP	Infections 
 MedDRA SOC infections and infestations 	
 
 AE011SP	Serious Infections 
 serious events in MedDRA SOC infections and infestations 	
 
 AE012SP	Opportunistic Infection 
 from Roche standard AEGT Opportunistic Infections 	
 
 AE014SP	Cardiac events MedDRA SOC "Cardiac Disorders"	
 
 AE015SP	Malignancies 
 preferred terms in the Malignant or Unspecified Tumors SMQ (Wide) 	
 
 AE016SP	NCI CTCAE grade 3 and 4 events, using separate sections for each grade	
 
 AE018SP	Events other than IRR occurring during or within 24 hours of a rituximab Infusion by relationship to treatment	
  
	ID	Subset	AE005SP	Events resulting to death (Stream Template: AET07)	AE006SP	SAEs	AE007SP	SAEs assessed as related to the study drug	AE008SP	Events leading to discontinuation of study medication	AE009SP	Events leading to a study medication dose modification	AE010SP	Infections 
 MedDRA SOC infections and infestations 	AE011SP	Serious Infections 
 serious events in MedDRA SOC infections and infestations 	AE012SP	Opportunistic Infection 
 from Roche standard AEGT Opportunistic Infections 	AE014SP	Cardiac events MedDRA SOC "Cardiac Disorders"	AE015SP	Malignancies 
 preferred terms in the Malignant or Unspecified Tumors SMQ (Wide) 	AE016SP	NCI CTCAE grade 3 and 4 events, using separate sections for each grade	AE018SP	Events other than IRR occurring during or within 24 hours of a rituximab Infusion by relationship to treatment
	ID	Subset																									
	AE005SP	Events resulting to death (Stream Template: AET07)																									
